## **Specific Aims**

Psychiatrically hospitalized Veterans are estimated to be at 40-50 times the risk for suicide than the general population in the year following discharge.  Despite their elevated risk, there are no clinical studies testing suicide interventions that are tailored to the population. To initiate a program of research that will address this need, we will conduct a randomized controlled trial (RCT) to examine the efficacy of Motivational Interviewing to Address Suicidal Ideation (MI-SI) plus TAU on suicidal ideation (SI) when compared to TAU alone. The study will include 140 high-risk Veterans who are hospitalized on a VA psychiatric inpatient unit. "High-risk" will be defined as scores over 2 on the Beck Scale for Suicidal Ideation (SSI), which prospectively predicts suicide. 

All participants will receive a baseline assessment of SI, suicidal behavior, and risk factors for suicide. Half will be randomized to MI-SI plus TAU and half to TAU alone. Participants in the MI-SI group will receive two sessions of MI-SI during their hospitalization plus one MI-SI telephone booster session in the month following discharge, in addition to TAU. All participants will be asked to complete telephone follow-up assessments at 1, 3 and 6 months after discharge. The primary outcome is change in the severity of SI. In exploratory analyses we will also examine the impact of MI-SI on treatment engagement, and treatment engagement as a mediator of the impact of MI-SI on change in the severity of SI.

The impact of the intervention on suicide risk during hospitalization is also of critical importance. In exploratory analyses, we will examine the effect of MI-SI on the severity of SI during the inpatient stay. Additionally, MI has been found to impact clients' in-session talk about making changes, which is associated with treatment outcome. In participants who receive MI-SI, we will examine the impact of in-session living talk (or talk associated with interest in living) and suicide talk (or talk associated with interest in suicide) on the severity of SI during hospitalization.

**Aim 1:** To conduct a randomized controlled trial (RCT) of 140 participants who are at high-risk for suicide. Participants will be randomized to receive MI-SI plus TAU, or TAU alone.

**Aim 2:** To evaluate whether MI-SI plus TAU results in significant reductions in suicidal ideation (SI) and increases in treatment engagement when compared to TAU alone.

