#### **Restatement of Aims**

**Aim 1:** To conduct a randomized controlled trial (RCT) of 140 participants who are at high-risk for suicide. Participants will be randomized to receive MI-SI plus TAU, or TAU alone.

**Aim 2:** To evaluate whether MI-SI plus TAU results in significant reductions in suicidal ideation (SI) and increases in treatment engagement when compared to TAU alone.

Primary Hypothesis: Participants who receive MI-SI plus TAU will report greater reductions in SI over follow-up, than participants who receive TAU alone.

Exploratory Hypothesis 1: Participants who receive MI-SI plus TAU will engage in more treatment over follow-up than participants who receive TAU alone.

Exploratory Hypothesis 2: Treatment engagement over follow-up will partially mediate the impact of MI-SI on SI.

**Aim 3:** To evaluate improvements during hospitalization.

Exploratory Hypothesis 3: Participants who receive MI-SI plus TAU will report greater reductions in SI during hospitalization, than participants who receive TAU alone.

Exploratory Hypothesis 4: In participants who receive MI-SI plus TAU, in-session living talk will be positively associated with reductions in SI during hospitalization.

Exploratory Hypothesis 5: In participants who receive MI-SI plus TAU, in-session suicide talk will be negatively associated with reductions in SI during hospitalization.

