### **Participants**

Participants will include 140 Veterans recruited from the Acute Psychiatric Inpatient Unit. Pilot data suggests that we will screen 320 patients to identify 140 participants. A sample size of 140 would provide up to 28 participants for training and piloting, and 112 participants for the RCT. The sample will be predominantly male and white non-Hispanic, though females and minorities will be eligible. 

Inclusion criteria. 1) Veteran status, 2) admitted to the unit, 3) age 18 and over, 4) English speaking, 5) able to understand the study and provide informed consent, 6) clinically cleared to participate (e.g., not violent), 7) receiving (or will receive) health care from a VA facility in upstate NY and 8) at increased risk for suicide (SSI > 2)

**Exclusion criteria.** 1) current psychosis, 2)

[figure not shown]
current mania, 3) dementia, 4) prisoner status, and 5) being inaccessible and discharged from the unit less than 48 hours after being identified by study staff.

**Estimated Flow.** Pilot data suggests that we can recruit approximately 0.54 participants per week. At this rate, we will recruit an estimated 112 participants in 4 years (208 weeks). Retention at 2 months using face-to-face assessments was 85%. The face-to-face assessment was changed to a telephone assessment to expand the catchment area to improve recruitment and increase retention. Assuming 80% retention at 6-month follow-up, we will have data from 90 Veterans.

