MI-SI Training. Training will consist of sixteen hours. It will consist of 8 hours of training in general MI followed by eight hours of MI-SI training. Training modalities include listening to power-point presentations, selected readings from the MI text  and the MI-SI manual (included in Appendix), MI exercises, and listening to and discussing recorded examples of MI-SI. The PI will observe the first two interviews to ensure that therapists meet MITI fidelity criteria and provide corrective feedback. Additional training activities will be scheduled as necessary.

MI-SI Supervision. An RCT evaluating methods for training MI clinicians found that ongoing coaching and/or feedback is needed to maintain proficiency in MI.  The PI will provide weekly supervision for MI-SI clinicians, focusing on promoting the fidelity of MI-SI by discussing

difficult cases, listening to and discussing recorded MI-SI interviews, and reviewing MI materials and publications.

**Interview Coding and Training.** MI-SI sessions will be recorded and coded for fidelity using the MITI,  which requires specialized training.

MITI Coding and Training. The MITI is a behavioral coding system that is used to code 20-minute samples of tape for adherence to MI principles (e.g. empathy, autonomy support) and use of specific MI techniques (e.g. reflections, open questions). Summary values from coded interviews will be used to assess fidelity,  and provide material for supervisory sessions. A random selection of interviews will be double-coded and inter-rater reliability will be computed using inter-class correlation coefficients. 

The PI will provide MITI training to the research assistants who are coding the MI-SI therapy sessions. The protocol that will be used is identical the one use by [name]., an MI Training expert who trained coders for Project MATCH,  and trained the PI. Training will consist of eight hours and include reviewing the MITI coding scale, coding MI interviews and comparing the codes to "gold standard" codes available on the MI website,  and coding recordings of MI-SI interviews. Coders will be considered reliable when they achieve reliabilities of good or better (ICC > .60) on 80% of MITI codes. 

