### **Analytical Plan**

**Data Preparation.** All data will be screened for missing data, outliers, non-normality, non-linearity, and non-homoscedasticity. A combination of statistics and graphic representations will be used to complete these screens. Specifically, missing values analyses, descriptive analyses, frequencies, scatter plots and histograms will be used. The assumptions underlying the proposed statistical analyses will also be tested, which may lead to data transformations or the use of more appropriate statistics. Additionally, imbalances in important covariates between randomized groups will be tested at baseline, which may lead to the identification of covariates to be included in the analyses. Findings will be used to fine-tune the analytical plan if statistical assumptions are unmet or model fit is poor. All analyses will be based on an intent-to-treat approach, analyzed as randomized, include all available data, use multiple imputation for missing data if appropriate, and use one-tailed tests with p < .05 as the cutoff for statistical significance. The study is not powered to test exploratory hypotheses, and we therefore do not

expect to detect significant differences between groups. If the analyses are reported as part of the primary RCT, we will use a p-value of .01 to define statistical significance.

**Aim 2:** To evaluate whether MI-SI plus TAU results in significant reductions in suicidal ideation (SI) and increases in treatment engagement when compared to TAU alone.

Primary Hypothesis: Participants who receive MI-SI plus TAU will report greater reductions in SI over follow-up than participants who receive TAU alone.

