Power Analysis: Recruitment will provide data on 112 participants. Assuming a retention rate of 80%, data on 90 participants will be available at the 6 month follow-up. To estimate the statistical power afforded by 90 participants for the severity of SSI, power analyses were conducted using STATA 11 101 "sampsi2" package, which uses calculations based on Frison and Pocock model. 102 Specifying method of analysis (change), number of baseline assessments (1), number of post assessments (3), correlation between baseline and follow-up scores (r = .50), correlation between follow-up scores (r = .70), and standard deviation (sd = 8.4) for the outcome variable using Frison and Pocock's recommendations and our pilot data. we would have .94 power to identify a 5-point difference in mean SSI scores between treatment arms, .81 power to identify a 4-point difference, and .60 power to identify a 3-point difference. The study would therefore be adequately powered to find an effect size of .5 for the primary outcome. If there is concern that the experimental intervention caused harm and the trial is not stopped, we will conduct two-sided analyses instead of the one-sided analyses we proposed. Power analyses suggest we will have .88 power to identify a 5-point difference, .71 power for a 4-point difference, and .47 power for a 3-point difference with the proposed 90 participants (45 in each group), indicating that the trial will still be fairly well powered.

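### Do the training and piloting patients (up to 28 of the 140) belong in the primary analysis?

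*Combined protocol and SAP*

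**What the plan says.** All references are to the combined protocol and SAP.

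- **Specific Aims:** "The study will include 140 high-risk Veterans who are hospitalized on a VA psychiatric inpatient unit", and then "Half will be randomized to MI-SI plus TAU and half to TAU alone".
- **Specific Aims and Restatement of Aims, Aim 1:** "To conduct a randomized controlled trial (RCT) of 140 participants who are at high-risk for suicide".
- **Participants:** "A sample size of 140 would provide up to 28 participants for training and piloting, and 112 participants for the RCT". The Estimated Flow paragraph of the same section forecasts 112 recruits over 208 weeks and data from 90 at 6 months.
- **Analytical Plan, Data Preparation:** "All analyses will be based on an intent-to-treat approach, analyzed as randomized, include all available data". This is the only rule on who is analysed. It gives no number and does not mention training cases.
- **Power Analysis:** "Recruitment will provide data on 112 participants". It assumes 80% retention, giving 90 participants, 45 in each group.
- **MI-SI Training:** "The PI will observe the first two interviews to ensure that therapists meet MITI fidelity criteria and provide corrective feedback", followed by "Additional training activities will be scheduled as necessary".

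**The concern.** The aims describe 140 patients, half in each arm, and the analysis rule keeps everyone as randomised. Taken together and literally, that puts 140 in the primary analysis. The Participants and Power Analysis sections count 112. The training allotment is given as a ceiling, and nothing states whether those patients are randomised, how they are marked, or that they are left out. Up to 28/140 = 20% of enrolled patients therefore seem to have no written status.

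Two things would be at stake. First, therapists still in training might deliver a weaker intervention, so including their cases could dilute the effect. Second, if the analysis set were settled after outcomes were known, the one-sided test at .05 would no longer hold its level.

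**Working it through.** **Inputs.** From the Power Analysis: change-score method, one baseline and three follow-up assessments, baseline-to-follow-up correlation .50, correlation among follow-ups .70, SD 8.4, retention 80%. From Data Preparation: one-sided .05. From Participants: 140 = 112 + 28, and 0.54 recruits per week for 208 weeks.

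**Step 1. Which total do the working sections use?**
- Recruitment: 0.54 × 208 = 112.3, stated as 112.
- Retention: 112 × .80 = 89.6, stated as 90 (45 per arm).
- Split: 140 − 112 = 28.

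All three agree with an RCT of 112. At 0.54 per week, 140 would need 140/0.54 ≈ 259 weeks, which is longer than the 208 planned.

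**Step 2. Reproduce the stated power.** The variance factor for the change in mean score is (1 + 2 × .70)/3 + 1 − 2 × .50 = .80. With 45 per arm, SE = 8.4 × √(.80 × 2/45) = 1.584. One-sided power is Φ(δ/SE − 1.645).

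| Difference | Stated | Reproduced |
|---|---|---|
| 5 points | .94 | .935 |
| 4 points | .81 | .811 |
| 3 points | .60 | .598 |

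The two-sided figures also reproduce: .884, .714 and .474 against .88, .71 and .47. The power statement is therefore correct for 112 and was built on it.

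**Step 3. What if all 140 were analysed?** 140 × .80 = 112, or 56 per arm, so SE = 8.4 × √(.80 × 2/56) = 1.420. Suppose all 28 are randomised 1:1 and show a fraction f of a true 4-point effect. The documents give no value for f, so this is an assumption, shown over its range. The average difference is 4 × (112 + 28f)/140.

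| f | Average difference | One-sided power |
|---|---|---|
| 0 | 3.2 | .729 |
| .5 | 3.6 | .813 |
| 1 | 4.0 | .879 |

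At half the effect, power is practically the planned .81. A real loss requires training cases with almost no benefit.

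**Step 4. The error rate if the set were chosen afterwards.** The two test statistics correlate at √(112/140) = .894. With no true effect, the chance that at least one exceeds 1.645 is 1 − Φ₂(1.645, 1.645; .894) = .069. With fewer training cases it is smaller: .058 for 4 and .061 for 8. Allowing the best of every cut-off from 0 to 28 excluded cases gives .090 (1,000,000 simulated trials). Each figure presupposes that the cases are randomised, followed up, and assigned to a set once results are known. If either set is fixed in advance, the error rate is .05.

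**Step 5. Set the passages side by side.** The Participants section is the only place that says what the 140 consists of, and it lists training and piloting separately from the RCT. Analysis as randomised then applies to those randomised into that RCT. If the training cases are not randomised, the rule leaves them out without further wording. If some are, the split in Participants still places them outside the trial whose hypothesis is tested. The MI-SI Training text concerns therapist supervision. It does not mention the 28 patients or set any boundary for them, so it does not support the idea of a movable cut-off.

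**The case for a change.** The strongest case for a change is that Aim 1 twice calls the trial an RCT of 140 whose participants will be randomised, and that the analysis rule would then keep all of them. The Randomization section describes a single set of sealed envelopes with no separate training list, and the recruitment log has no field for a training case. Because the allotment is a ceiling, even a reader who accepts 112 cannot tell which cases are out, or how many. The forecast of about 112 recruits in total leaves no room for another 28, which could create pressure to count training cases. With a true 4-point effect, the 112 and 140 analyses would disagree on significance in 10% to 13% of trials, and a sentence or two would close the matter.

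Part of this stands. The wording of Aim 1 does not match the Participants section, and no exclusion is written out. The rest does not follow. A headline figure in the aims does not override the one passage that itemises it, especially when the forecast and the power analysis agree with that passage. The disagreement rate shows that two different analysis sets can give different answers. It does not show that the plan leaves the choice open until results are known. The clause allowing the analytical plan to be fine-tuned concerns unmet statistical assumptions and poor model fit, not who is analysed.

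**Conclusion.** No change to the plan follows. The mismatch between 140 and 112 is a clerical slip in Aim 1, where total enrolment is called the size of the RCT. The unwritten exclusion is a gap that an analyst would fill sensibly from the Participants section: training and piloting cases are not RCT participants and do not enter the primary analysis.

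On that reading there are 112 randomised, 45 per arm with data at 6 months, and a 4-point one-sided power of .811 against the stated .81. No stated figure is wrong. The adverse figures all rest on conditions that the documents do not contain: .729 on all 28 being randomised, analysed and showing no effect, and .069 or .090 on a choice of analysis set after results are seen.

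The conclusion assumes that the specific breakdown governs over the headline total, and that training cases are identified as such when they are enrolled, which is the ordinary meaning of setting patients aside for training.

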All 13 participants were male, average age was 46.77 (10.49), 9 (69.2%) were non-Hispanic white, 7 (53.8%) had seen combat, 8 (61.5%) had a previous suicide attempt, and 5 (38.5%) had more than one. Chart reviews indicated that 11 of 13 (85%) had mood disorders, 10 (77%) anxiety disorders, 7 (54%) substance use disorders, and 2 (15%) attention deficit disorders. All 13 had been engaged in mental health or substance use treatment in the year prior to admission. Findings showed that MI-SI was acceptable to participants. The mean (SD) CSQ-8 score was 3.58 (.40), indicating that they were "3 = mostly" to "4 = very satisfied".

Findings suggested that MI-SI has promise and is worthy of continued study. Pre-post effect sizes were computed using the formula: ES =  $(M_{pre} - M_{post})/SD_{pre}$  (Tables 1 and 2).  A standard version (last week) of the SSI was used at baseline and follow-up, and a modified version (past 48 hours) was used at post-treatment. Participants who received MI-SI experienced reductions in the severity of SI, with an effect size of 3.39 from baseline to posttreatment indicating an immediate reduction in SI. The effect size from baseline to follow-up was 1.95, indicating continued reduction. These effect sizes are recognized as clinically significant,  and compare favorably to TAU data collected by consultant [name]. In a study of 15 participants recruited primarily from inpatient units, with additional patients from the Emergency Department, Consult-Liaison, and Crisis Intervention services from an urban medical center, SSI scores fell 9 points from baseline to 60-day assessment. The reduction was almost half the 17.9-point reduction observed in this study. The percentage of participants whose SSI scores fell below the high risk threshold (< 3) was used to confirm clinical significance. Thirty-three percent of scores from baseline to post-treatment fell below the threshold (< 3), as did 64% of scores from baseline to follow-up. All participants attended one mental health or substance abuse treatment session after discharge. Of the 11 participants with follow-up data, 7 (64%) completed 4 or more sessions, which compares favorably to previously reported rates. 

Table 1. Post-treatment Outcomes for MI-SI Pilot Study (N = 9)

Measure	Baseline	Post-Treatment	Effect	% Below
	Mean (SD)	Mean (SD)	Size	Cutoff
SSI	27.56 (4.88)	11 (10.44)	3.39	33.33 < 3

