**Baseline Assessment.** To describe the sample, all participants will complete the baseline assessment that will include measures of depression, substance use disorders, PTSD, and trait anxiety as they have been found to increase risk for suicide in Veterans,  treatment engagement which is associated with suicide after discharge from psychiatric hospitalization,  insomnia which may be associated with suicide risk in Veterans,  anger is associated with increased suicide risk and may impact the effectiveness of MI based interventions for Veterans,  and previous suicidal behavior which is a robust predictor of suicide.  Although there are no measures of motivation to live, we are also interested in piloting a motivation to live measure as a potential risk factor. We are also adding three measures that assess mechanisms through which MI-SI may work and therefore serve as short-term outcomes. They will be used to describe the sample and may be controlled for in the analyses if there are differences between conditions.

- 1. Depression (9 items): The Physicians Health Questionnaire (PHQ-9)  is a reliable and valid self-report assessment of depressive symptoms that is used by VA. 
- 2. PTSD (17 items): The PTSD Checklist Civilian Version (PCL-C)  $^{58}$  is a reliable and valid self-report assessment of PTSD symptoms  $^{59}$  that is used with Veterans.  $^{60}$

- 3. Anxiety (21 items): The Beck Anxiety Inventory (BAI)  $^{61}$  is a reliable and valid self-report measure of anxiety.
- 4. Alcohol Use Disorders (10 items): Alcohol Use Disorders Identification Test (AUDIT)  $^{62}$  is a self-report measure designed to assess hazardous alcohol use that is reliable and valid in Veterans.  $^{63}$
- 5. Drug Abuse (10 items): A reliable and valid 10-item short-form of the Drug Abuse Screening Test (DAST)  $^{64}$  will be used to assess non-prescription drug abuse, not including alcohol abuse. The DAST has been used with Veterans.  $^{65}$
- 6. Substance Use Frequency past 90 days / Drug of Choice (12 items): The Substance Use Frequency Form (SUFF) is a measure that was developed by [name] to assess substance use frequency and drug of choice. It is based on questions commonly used in the substance abuse literature.  $^{66}$

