Maintaining Blind Outcome Assessments. In-hospital and post-discharge follow-up assessments will be conducted by research assistants who are blind to condition. The blind will be maintained by having research assistants who are not involved in the baseline and treatment phases of the study conduct the assessment by telephone from the CoE. After each outcome assessment, research assistants will be asked if they thought the participant was assigned to the experimental condition (MI-SI plus TAU), control condition (TAU alone), or don't know which condition the participant was assigned to. They will also be asked how they decided the condition to ensure that the blind was indeed broken and the determination was not due to extraneous information such as positive outcome, which would presumably lead a research assistant to guess the MI-SI plus TAU over TAU alone. If blinding was successful, research assistants will not be able to determine assignment at a better than chance rate. 

Randomization. Prior to randomization, participants will be stratified by SSI scores to increase the probability of balanced assignment, which may decrease the probability of a Type 1 error and increase power.  Stratification will be based on a median split using data from pilot study #1. Participants who score below 24 will be in the lower SSI group, and those who score 24 and above will be in the higher SSI group. A blocked randomization procedure using block sizes of 4 and 6 participants will also be used to assure no significant imbalance between the numbers of participants in each condition at any time, and to protect against guessing condition assignment.  Randomization will occur prior to the start of the trial and the results will be recorded in sealed envelopes. After the baseline assessment, the researcher will choose the next envelope (within the strata and block) to determine the participant's assignment. The researcher will then inform the study therapist that a participant has been randomized to receive MI-SI.

**Treatment Conditions.** Participants will be randomized to MI-SI plus TAU or TAU alone.

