Primary Analysis 1: An over-dispersion Poisson generalized linear mixed model (GLMM) with maximum likelihood estimation will be used to examine the effect of MI-SI on the severity of SI at 1, 3, and 6 months follow-up. GLMM was chosen because random effects are added to the model to account for repeated measures within subjects. An over-dispersion Poisson GLMM will be used because the SSI is bounded at zero and had a standard deviation larger than the mean at follow-up in our pilot data, indicating over-dispersion. If data do not meet the assumptions of a Poisson distribution, we will use a negative binomial or zero-inflated negative binomial. The benefit of using maximum likelihood estimation is that it yields unbiased estimates in the presence of missing data, if data are missing at random. Because participants may receive one or two sessions of MI-SI, and the change pattern may not be linear over time, we will test sessions of MI-SI, time of assessment, and their interaction in follow-up analyses. As an added measure of clinical significance, we will report the number of participants in each group who fall below the two-point cut-off.

Because the presence of any suicidal behavior (i.e., attempted suicide, interrupted attempts, preparatory behavior) is an important outcome, we will use a mixed effects general logistic model to examine the effect size of MI-SI on the incidence of suicidal behavior as measured by the C-SSRS over follow-up assessments.

Exploratory Hypothesis 1: Participants who receive MI-SI plus TAU will engage in more treatment over follow-up than participants who receive TAU alone.

Exploratory Analysis 1: Multivariable logistic regression will be used to examine the effect of MI-SI on treatment engagement. The Hosmer-Lemeshow statistic will be used to evaluate model fit, and odds ratios with 95% confidence intervals will be derived using the method of maximum likelihood.  Because participants may receive one or two sessions of MI-SI, we will conduct a sensitivity analysis examining the number of MI-SI sessions as a predictor of treatment engagement. Because this is an underpowered exploratory analysis, we will also conduct secondary analyses using other definitions of treatment engagement such as number of sessions attended.

We will also examine the impact of the intervention on use of the Safety Plan coping strategies. To test treatment differences, we will use a multivariable logistic regression.

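### Primary Analysis 1 does not say how baseline SSI or the SSI randomisation stratum enters the model; both should be pre-specified as fixed effects

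*Combined protocol and SAP*

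**What the plan says.** Under General Procedures, Randomization, "participants will be stratified by SSI scores to increase the probability of balanced assignment". The cut is at 24, taken from the median in Pilot Study #1, with blocks of 4 and 6. Greater power is one of the reasons given for stratifying.

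Under Analytical Plan, Primary Analysis 1 is an over-dispersed Poisson mixed model used "to examine the effect of MI-SI on the severity of SI at 1, 3, and 6 months follow-up". On structure it says "GLMM was chosen because random effects are added to the model to account for repeated measures within subjects". No covariate is named.

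Covariates are covered elsewhere, always conditionally:

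- Data Preparation: "imbalances in important covariates between randomized groups will be tested at baseline, which may lead to the identification of covariates to be included".
- Baseline Assessment: the measures in that battery "may be controlled for in the analyses if there are differences between conditions". SSI is not in that list; it belongs to the Screening Assessment.
- Treatment Engagement (TSR-6): baseline service use is compared between arms to decide whether to account for it.
- TAU: suicide-related usual care is to be controlled for if the arms differ on it.

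None of these names SSI or the stratum. Specific Aims nevertheless describes the primary outcome as change in severity, and the Power Analysis paragraph uses the change method with one baseline assessment and a "correlation between baseline and follow-up scores (r = .50").

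**The concern.** The design balances on SSI and the planning uses baseline SSI, but the stated primary model does not carry either forward. When randomisation is stratified on a prognostic variable and the analysis leaves it out, the model's standard error still includes between-stratum variation that the design has removed from the treatment comparison. The reported standard error is then too large, the test is conservative and power is given up.

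The conditional rules do not repair this. Stratifying on SSI is what prevents an SSI imbalance from appearing, so the variable most worth adjusting for is the one least likely to be selected. Other covariates could still enter through baseline significance tests, which leaves the primary model undefined until data are seen.

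The plan has little power to spare: by its own figures, .60 for a 3-point difference, and .71 for 4 points under the two-sided fallback.

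**Working it through.** **Inputs (Power Analysis paragraph).** SD 8.4; correlation among follow-ups .70; baseline to follow-up correlation r = .50; three follow-ups; 45 per arm; one-sided 5% level.

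**Reproducing the stated power.** For the mean of three follow-ups, in units of SD²:

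- Follow-up only: V = (1 + 2 × .70)/3 = .80
- Change: V = .80 + 1 − 2 × .50 = .80
- SE = 8.4 × √(2 × .80/45) = 1.584

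One-sided power for 5/4/3 points is .935/.811/.598 (stated .94/.81/.60). Two-sided power is .884/.714/.474 (stated .88/.71/.47). At r = .50 the two variances coincide, so the stated figures also hold for a model of follow-up scores alone.

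**What omission does at r = .50.** With a roughly normal baseline split at its median, the stratum correlates .50 × √(2/π) = .40 with each follow-up.

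- True variance of the unadjusted contrast under stratified randomisation: .80 − .40² = .64
- Variance the unadjusted model reports: .80, a ratio of .80/.64 = 1.25
- Actual one-sided size: 1 − Φ(1.645 × √1.25) = .033
- Variance adjusting for continuous baseline: .80 − .50² = .55

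Adjustment therefore cuts the reported variance by 1 − .55/.80 = 31%, but the true sampling variance by only 1 − .55/.64 = 14%.

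**Simulation over r.** Normal scores, 90 participants, blocks of 4 and 6 within a median-split stratum, t test on the mean follow-up. The adjusted model has arm, baseline and stratum. There were 20,000 null trials, 10,000 trials at 4 points and 6,000 at 3 points per value of r.

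| Baseline r | .2 | .3 | .4 | .5 |
|---|---|---|---|---|
| One-sided size, unadjusted | .046 | .044 | .040 | .034 |
| One-sided size, adjusted | .048 | .049 | .051 | .051 |
| 4 points, unadjusted | .81 | .82 | .82 | .83 |
| 4 points, unadjusted, size-matched | .82 | .83 | .85 | .87 |
| 4 points, adjusted (same when size-matched) | .82 | .84 | .87 | .91 |
| 3 points, unadjusted | .59 | .59 | .59 | .61 |
| 3 points, adjusted | .60 | .63 | .67 | .73 |
| 4 points, two-sided, unadjusted | .70 | .71 | .72 | .72 |
| 4 points, two-sided, adjusted | .72 | .75 | .80 | .85 |

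Size-matched means that each test uses its own simulated 5% null cutoff. At r = .5 the raw 4-point gain is .91 − .83 = .08. About half of it, .91 − .87 = .04, is real precision; the rest is removal of conservatism.

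**Would an imbalance test bring SSI in?** At p < .05 such a test fired in about 0.1-0.2% of trials. The plan states no threshold for it, so .05 is an assumption.

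**Dependence of the planned power on r.** By the formula above, 4-point one-sided power under the change method is .60/.66/.73/.81 at r = .2/.3/.4/.5. Follow-up-only power stays at .81.

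**The planned count model.** One simulation used an over-dispersed Poisson mixed model at the pilot's floor, where 62-64% of scores fell below 3. It assumed 5/10/20% missing at 1, 3 and 6 months. The reported squared standard error fell 18% at r about .29 and 35% at r about .44. One-sided power at a 3.9-point difference went from .77 to .82 and from .80 to .87. There were only 124 trials per scenario under the alternative (power SE about .035) and no clear size-matched gain. Two-tail type I error (nominal .10, SE about .02) was .054 unadjusted and .091 adjusted at the lower r, and .081 and .134 at the higher r.

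**The case against.** The strongest reply is that this is under-specification, not a decision to leave baseline out. Primary Analysis 1 is silent; the outcome is called change, the hypothesis speaks of reductions, and power uses the change method, so baseline SSI was probably meant to enter somehow. That stands as a description: the follow-up-only model quantified above is one reading of the text. It does not close the gap, because no passage says how baseline enters, and a change analysis would not by itself account for the stratum.

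Second, the clean figures are for normal scores and a t test, whereas the plan uses a count model with a heavy floor (in the pilot, scores under the threshold of 3 at follow-up: "as did 64% of scores from baseline to follow-up"). This stands. In the count simulation conservatism did not grow with r as it does on the linear scale, and some of the apparent gain at the higher r may be excess size in the adjusted model. Simpler count models (quasi-Poisson and negative binomial on summed visits) favoured adjustment on power but did not hold exact size. The direction is plausible; the amount is unknown.

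Third, the gain depends on r. The value .50 is a planning input, and Pilot Study #1 reports no baseline to follow-up correlation. Size-matched, the 4-point gain at r = .2-.3 is .01 or less. This also stands.

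Fourth, the stratum is a dichotomised SSI and adds almost nothing once continuous baseline is in: in linear runs it changed 4-point power by no more than .005. It is kept to match the design, not for power.

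**Conclusion.** The point holds as a pre-specification gap with an efficiency cost. The primary model should name baseline SSI and the stratum; at present neither is named, and the conditional rules would almost never bring SSI in. This should be changed, but it is not a fatal flaw.

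A reader might infer more than the documents support:

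- *The stated power is wrong.* It reproduces to two decimals, and at r = .50 it applies equally to an unadjusted follow-up model.
- *False positives are inflated.* On the linear scale the unadjusted test errs the other way, with one-sided size .034 to .046.
- *The plan rules out adjustment, or allows it only for baseline imbalance.* It does neither. It is silent on SSI, and the TAU paragraph also allows adjustment for care received.
- *Power in this trial would rise from .83 to .91.* That is the linear result at r = .5, half of it from restoring nominal size.

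On the linear scale the raw 4-point gain runs from about .01 at r = .2 to .08 at r = .5, and the size-matched gain from .00 to .04. These figures assume normal scores, a median-split stratum, 45 analysed per arm and the plan's SD and follow-up correlation. The gain in the over-dispersed Poisson model is not established. The case for changing the text rests mainly on matching analysis to design and fixing the primary model in advance.

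**What to change.** In Primary Analysis 1, state that baseline SSI and the randomisation stratum are fixed effects regardless of any imbalance test. Enter baseline SSI as a continuous term on a log or similar scale suited to the log link. Most of the gain comes from this term.

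Name the SSI version. Randomization says only SSI scores, while the Screening Assessment lists past-week, worst-point and 48-hour versions. In the pilot that supplied the cut of 24, "A standard version (last week) of the SSI was used at baseline and follow-up". The covariate should be the version used for stratification and follow-up.

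In Data Preparation, Baseline Assessment, the TSR-6 item and the TAU paragraph, say that baseline significance tests and observed differences between arms do not select covariates for the primary model. Any such adjustment belongs in a labelled sensitivity analysis.

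In the Power Analysis paragraph, replace the change method with one that matches the adjusted model, and show power over a baseline correlation of about .2 to .5.

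The cost is wording in those places and two model degrees of freedom. No new data are needed: an SSI score above 2 is an inclusion criterion, so SSI is measured on everyone before randomisation.
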